6.3 Clinical Benefit Rate (CBR)

CBR is estimated based on the crude proportion of patients in each treatment arm whose best overall response during the course of study treatment is CR, PR or SD lasting for at least 24 weeks (measured from the date of randomization to the last date where SD is reported).

$$CBR_{RECIST\ 1.1} = \frac{\# \text{ of patients with best confirmed overall response as CR/PR/ SD lasting for} \geq 24 \text{ weeks}}{\text{Total number of patients}}$$

Similarly, CBR is calculated based on irRECIST as below:

$$CBR_{irRECIST} = \frac{\# \text{ of patients with best confirmed overall response as irCR/irPR/irSD lasting for} \geq 24 \text{ weeks}}{\text{Total number of patients}}$$

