13.2 Phase 2 Interim Efficacy Analyses

The sample size and number of PFS failures were adjusted using the O'Brien -Fleming group sequential procedure to account for 1 planned interim analysis of PFS after 45 events (75% information). It is projected that 75% and 100% of total information will be reported at approximately 12 and 18 months, respectively.

The interim analysis will be performed to support the Sponsor's product development plans and ongoing resourcing activities. Although there are no plans to terminate the study early because of early evidence of superior efficacy for the combination treatment, the significance levels at the interim analysis and final analysis will be adjusted to maintain control of the overall type I error rate for multiple testing of PFS (O'Brien 1979).

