5.2.2 Phase 2 Expansion Phase

The following assumptions are made:

- Patients in the control arm have true median PFS of 4 months
- Patients in the experimental arm have true median PFS of 7 months (under exponential distribution, true PFS hazard ratio of 0.57)
- Expected accrual duration will be 9 months and an additional 9 months of follow-up. The α type I error rate is set to 10% (1-sided)
- The β type II error rate is set to 20% (i.e. the power of the trial will be 80%)

Under these assumptions, 70 patients (35 per arm) will be enrolled in the trial, which is projected to result in 60 PFS failures, defined as documented disease progression by RECIST 1.1 or death due to any cause without documented disease progression beforehand, within approximately 18 months of the first patient randomized.

It is anticipated that the number of patients that drop out without PFS failure will be low (2-3%). Depending on the actual number of such dropouts, the number of patients accrued maybe increased by 6-10 patients to accommodate for a higher-than-expected number of dropouts.

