5.4.2 Phase 2 Expansion Phase

The following analyses are planned:

- An interim safety analysis will be performed following the completion of Cycle 1 for the first 20 patients enrolled in the Phase 2 expansion phase, and will utilize a Data Safety Monitoring Board (DSMB).
- An interim efficacy analysis will be performed when 45 PFS events have observed. Data cut-off for the analysis will be based on the calendar date of the 45th PFS event (per RECSIT 1.1). Safety and secondary endpoints will also be evaluated. The same data cut-off used for the PFS analysis is also used for the corresponding analysis of safety and secondary endpoints.
- Primary efficacy analysis will be performed when 60 PFS events are observed. Similarly, the data cut-off for the primary analysis will be based on the calendar date of the 60th PFS event. Safety and secondary endpoints will coincide with the primary PFS analysis.
- End of study analysis for safety and OS analysis will be performed when the last patient terminates study treatment.

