7. STUDY POPULATION

7.1 Full Analysis Set (FAS)

The **Full Analysis Set (FAS)** includes all patients who were enrolled (for Phase 1b) or randomized (for Phase 2) to study treatment, regardless of whether they actually received study medication. All efficacy analyses will be evaluated based on data from this population set according to the treatment group they were assigned to at registration/randomization and based on the strata they were originally assigned to at the time of randomization. This population set will be identified using the FASFL (Full Analysis Set Population Flag) as defined in Subject-Level Analysis Dataset (ADSL) according to Analysis Data Model (ADaM).

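### At the 45-event interim, CBR keeps every randomized patient in the denominator, so recently randomized patients in ongoing stable disease are scored as failures

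*SAP*

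**What the plan says.** **Definition.** SAP 6.3 takes CBR as a crude proportion. The numerator is best overall response of "CR, PR or SD lasting for at least 24 weeks (measured from the date of randomization to the last date where SD is reported". The denominator is "Total number of patients". Efficacy is analysed in the FAS, which "includes all patients who were enrolled (for Phase 1b) or randomized (for Phase 2) to study treatment" (SAP 7.1).

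**Timing.** SAP 5.4.2 states: "An interim efficacy analysis will be performed when 45 PFS events have observed". Of that analysis it adds: "Safety and secondary endpoints will also be evaluated". It also fixes the data: "The same data cut-off used for the PFS analysis is also used for the corresponding analysis of safety and secondary endpoints". CBR is a secondary endpoint (SAP 4.2.2), so it is included.

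**Calendar.** SAP 5.2.2: "Expected accrual duration will be 9 months and an additional 9 months of follow-up". Protocol 13.2: "It is projected that 75% and 100% of total information will be reported at approximately 12 and 18 months, respectively".

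**What is absent.** SAP 6.1 and 6.4 have censoring rules for patients with incomplete PFS or OS follow-up. For CBR, SAP 10.8.3 only refers to the ORR methods, and SAP 9.4 does not impute missing data unless otherwise specified. Nothing sets a minimum follow-up for CBR or defers it to the 60-event analysis.

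**The concern.** Accrual is planned to end at month 9 and the interim is expected about three months later, but stable disease must last 24 weeks (about 5.5 months) to count. For a patient randomized shortly before the cut-off and still stable, the outcome is simply not known yet. The formula nonetheless leaves her out of the numerator and keeps her in the denominator.

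Interim CBR would therefore be too low in both arms. If entinostat prolongs PFS, more of its recent patients are still stable, so its arm loses more points. Protocol 13.2 says the interim is run to support the sponsor's development and resourcing plans, and SAP 8 has the DSMB review it. A CBR that is low only because follow-up is short could be misread there, and it would not be comparable with CBR at the 60-event analysis.

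**Working it through.** **Inputs.** 70 patients, 35 per arm; 9 months of accrual; exponential PFS with medians of 4 and 7 months (SAP 5.2.2, Protocol 13.1.2). Interim at 45 of 60 events (Protocol 13.2). 24 weeks = 168/30.4375 = 5.52 months. Assumed here: uniform accrual, no dropout, and CBR approximated by PFS of at least 24 weeks.

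**Plan's own figure.** With hazard ratio 4/7, one-sided 0.1 and O'Brien-Fleming looks at 75% and 100% information, 80% power needs 59.6 events, and 60 events give 80.2%. The stated 60 events are reproduced.

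**When the interim falls.** Expected events per arm at month t ≥ 9 are (35/9) × [9 − (e^(−λ(t−9)) − e^(−λt))/λ], with λ = ln 2/median. Month 12 gives 24.5 + 17.8 = 42.2 events. The 45th is expected at month 12.8.

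**Share randomized under 24 weeks earlier.** f = [9 − (t − 5.52)]/9.
- Month 12: 2.52/9 = 28% (19.6 of 70).
- Month 12.8: 19% (13.2 of 70).
- If events are dated at scheduled scans, the simulated interim averages month 13.6. The formula gives 10% there, and the average over simulated trials is 12%.

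**Recent and still progression-free.** Integrating e^(−λ(t−u)) over entry times u from t − 5.52 to 9 and dividing by 9 gives, at month 12.8, 8.4% of control and 11.9% of entinostat (about 3 and 4 of 35). At month 12 it gives 13.5% and 18.4%.

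**Effect on CBR.** With mature follow-up, S(5.52) = 38.4% and 57.9%. The formula yields (1 − f) × S:

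| Cut-off | Control | Entinostat | Difference | Ratio |
|---|---|---|---|---|
| Mature | 38.4% | 57.9% | 19.5 | 1.51 |
| Month 12.8 | 31.2% | 47.0% | 15.8 | 1.51 |
| Month 12 | 27.7% | 41.7% | 14.0 | 1.51 |

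At month 12.8 the bias is 38.4 − 31.2 = 7.2 points (control) and 57.9 − 47.0 = 10.9 points (entinostat).

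**Counting responders.** A confirmed CR or PR counts without the 24-week wait. The documents give no response rate for unselected patients, so these rates are assumptions (simulation, cut-off at the 45th event, average month 12.7):
- 10% vs 20%: 36.2% vs 54.4% (18.2 points) instead of 42.3% vs 62.7% (20.4).
- 10% vs 10%: 36.2% vs 50.6% (14.4) instead of 42.2% vs 60.2% (18.0).
- 20% vs 30%: 40.9% vs 58.1% (17.1) instead of 45.9% vs 65.1% (19.2).

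Across these, 6–8% of control and 8–11% of entinostat patients are undecided.

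**No treatment effect.** With both medians at 4 months the 45th event comes at month 11.0 and 39% are recent. Both arms shrink by the same factor and the expected difference remains zero.

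**60-event analysis.** At the projected month 18 the last patient has 9 months of follow-up, so f = 0. The modelled date under the alternative, month 20.4, is later still.

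**The case against.** **A reader might infer that about a quarter of patients are affected.** The documents do not support that as the central figure. The cut-off is the date of the 45th event, not month 12, and the plan's own assumptions give only 42.2 events at month 12. The share at the modelled date is 19%. Many of those patients have already progressed and are scored correctly, and confirmed responders count at once.

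**A reader might infer that the treatment comparison is generally diluted.** That is also too strong. SAP 10.8.2, which governs CBR, specifies a CMH test, per-arm intervals and relative-risk output, and names no risk difference. In this model the relative risk does not move. The odds ratio does, from 2.20 to 1.96. The absolute difference loses 19.5 − 15.8 = 3.7 points, against a standard error of the difference of about 11.5 points. Restricting to mature patients raises the ratio of difference to standard error only from 1.37 to 1.50, because patients are lost.

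**Nor do the documents tie a decision to interim CBR.** There is no plan to stop early for efficacy, and PFS at the same cut-off is analysed by Kaplan-Meier, which censors these same patients properly.

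All of this stands and limits the importance of the point. It does not remove it: the per-arm estimates carry a systematic shortfall that the SAP neither corrects nor flags.

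Protocol 13.5.5 times stable disease from treatment start to progression, whereas SAP 6.3 uses randomization to the last report of SD. These need reconciling, but neither clock can reach 24 weeks when follow-up is shorter than that.

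**Conclusion.** The point holds, for the interim only. As written, SAP 6.3 scores recently randomized patients in ongoing stable disease as CBR failures at the 45-event cut-off. About 19% of patients are recent at month 12.8 (range about 10–28% under the plan's alternative), and about 8% of control and 12% of entinostat patients are both recent and progression-free, fewer once confirmed responses are counted. Interim CBR is low by about 7 and 11 points on the 24-week PFS approximation. If the hypothesized effect is real, the absolute difference falls from about 19.5 to about 16 points (14 at month 12).

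These sizes rest on uniform 9-month accrual, exponential medians of 4 and 7 months and no dropout. Primary PFS and CBR at 60 events are untouched. The change is worth making because it is cheap; the trial's main inference does not depend on it.

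**What to change.** In SAP 5.4.2, 6.3 and 10.8.3, choose one:

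1. **Report CBR only at the 60-event analysis.** This is the simpler choice. The cost is having no interim CBR.
2. **Restrict interim CBR, identically in both arms, to FAS patients randomized long enough before the cut-off for the week-24 scan to have occurred.** Twenty-four weeks plus 3 days is not enough. Scans run from C1D1 (Protocol 6.1), which may be up to 3 business days after randomization (Protocol 9.1), and the scan window adds 3 days. Taking 3 business days as up to 5 calendar days over a weekend, the margin is 168 + 5 + 3 = 176 days (5.78 months). The SD clock must also credit a week-24 scan done within its window. Otherwise a scan 3 days early can fall at day 165, short of 168, and the patient stays undecided until week 30.

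Option 2 depends only on the randomization date, so the randomized comparison is kept. It removes [9 − (t − 5.78)]/9 of patients: about 22% at month 12.8, 31% at month 12 and 13% at month 13.6. Either option takes a sentence or two in the SAP.

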A treatment cycle is 3 weeks (21 days) in length. The dose of atezolizumab will be fixed at 1200 mg IV q 3 weeks (day 1 of each cycle) for all patients. Entinostat (during the Phase 1b Dose Determination Phase) and entinostat / placebo (during Phase 2, Expansion Phase) will be administered orally on days 1, 8 and 15 of each 21 day cycle. The Dose Determination Phase will begin with a starting dose (dose level 1) of entinostat 5 mg po weekly. If dose level 1 exceeds the MTD, then entinostat 3 mg po weekly (dose level -1) will be investigated. If dose level -1 exceeds the MTD, then entinostat 2 mg po weekly (dose level -2) will be investigated. Dosing is planned to be continuous unless interrupted for management of an adverse event. The entinostat dose determined appropriate for combination with atezolizumab will then be taken forward into the Phase 2 Expansion Phase of the study as the RP2D.

During treatment, patients will attend study center visits and have study evaluations performed on C1D1, C1D8, and C1D15; D1 and D15 of C2; and on D1 of each cycle thereafter. Patients will have radiological disease assessments performed within 28 days prior to the first dose of study drug, and then every 6 weeks (+/- 3 days) through week 36 (Weeks 6, 12, 18, 24, 30, 36) until unequivocal progressive disease. Patients remaining on study after week 36 will undergo radiological disease assessments every 9 weeks (+/- 3 days) until unequivocal progressive disease occurs. Disease will be assessed by computed tomography (CT), magnetic resonance imaging (MRI), and bone scans, as appropriate using the same method as used for the screening evaluation, and response will be assessed by the Investigator using RECIST 1.1.

Safety will be assessed during the study by documentation of AEs using United States (US) National Cancer Institute (NCI) Common Terminology Criteria for Adverse Events (CTCAE), version 4.03, clinical laboratory tests, physical examinations, vital sign measurements, electrocardiograms (ECGs), and Eastern Cooperative Oncology Group (ECOG) performance status. Adverse events of special interest (AESI) will be collected and reviewed in a manner consistent with serious adverse event reporting procedures.

Fresh tumor tissue core biopsy samples will be collected during the study as follows:

- During screening from all patients on a mandatory basis. Archival biopsies when available will also be collected for comparison.

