Blood for immune correlates is to be collected pre-dose on each of C1D1, C2D1, C2D15, C3D1 and at the end of treatment. Blood for protein lysine acetylation is to be collected pre-dose on C1D1 and C1D15. Patients will have radiological disease assessments performed every 6 weeks (+/-3 days) (Week 6, Week 12, etc.) beginning at C1D1, during study treatment through week 36 or until progressive disease. If progressive disease has not occurred by week 36, radiological assessments will then be done every 9 weeks (+/-3 days) until progressive disease. If a patient comes off study for reasons other than progressive disease, radiological assessments will continue at 6 week intervals until what would have been study week 36 and then switch to a 9 week interval, until progressive disease is radiologically documented. Disease will be assessed by computed tomography (CT), magnetic resonance imaging (MRI), and bone scans, as appropriate, and response will be assessed by the Investigator using irRECIST. The same imaging modality should be employed for all follow-up scans as was used at baseline.

Safety will be assessed during the study by documentation of AEs, clinical laboratory tests, physical examination, vital sign measurements, ECGs, and Eastern Cooperative Oncology Group (ECOG) performance status.

Within 7 days of the last dose of study treatment, all patients will complete an End of Treatment (EOT) visit, and a Safety Follow-up (F/U) visit will be required 30 days (+/- 3 days) thereafter.

After completion of the 30-day F/U visit, patients who have experienced progressive disease are to be contacted every 3 months thereafter for survival status and information regarding treatment regimens, until death or closure of the study by the Sponsor. Those patients who have not experienced progressive disease, will continue radiological disease assessments as noted above.

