For such patients, the progression or censoring date will be determined based on described conventions ([FDA 2007](#)). Sensitivity analyses will be performed to assess the impact of the different censoring mechanisms and deviations from the planned schedule of disease assessments ([Bhattacharya 2009; Stone 2011](#)).

ORR will be estimated based on the crude proportion of patients in each treatment arm whose best overall response during the course of study treatment is CR or PR. Tumor response will be assessed using irRECIST. Approximate 95% confidence intervals will be calculated by treatment arm for the true ORR. The inferential comparison of the observed ORRs will be made using the Cochran-Mantel-Haenszel chi-square test, stratified by the randomization stratification factors. The corresponding results without stratification will be reported as supplemental analyses.

DOOR will be calculated for patients who achieve CR or PR. For such patients, DOOR is defined as the number of months from the start date of PR or CR (whichever response occurs first) and subsequently confirmed, to the first date that recurrent or progressive disease is documented. The date of progression or censoring for DOOR will be determined using the conventions described for PFS. DOOR will be summarized descriptively for each treatment arm using the Kaplan-Meier method. Inferential comparisons between treatment arms for DOOR are not planned.

CBR will be estimated based on the crude proportion of patients in each treatment arm whose best overall response during the course of study treatment is CR, PR, or stable disease lasting for at least 24 weeks. Stable disease will be measured from the start date of study treatment until the criteria for progressive disease is first met. The analysis of CBR and its duration will be based on the methods described above for ORR and DOOR, respectively.

OS is defined as the number of months from randomization to the date of death (due to any cause). Patients who are alive or lost to follow-up as of a data analysis cutoff date will be right-censored. The censoring date will be determined from the patients' date of last contact or data analysis cutoff date, whichever date occurs first. The analysis of OS will be based on the methods described above for PFS.

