1. INTRODUCTION

This Statistical Analysis Plan (SAP) describes the detailed statistical methodology for executing the statistical analyses to assess the antitumor activity and safety profile of atezolizumab in combination with entinostat versus atezolizumab alone in treatment of advanced triple negative breast cancer (aTNBC) according to SNDX-275-0602 (TRIO025) protocol version 1.0.

Statistical analysis will be performed by TRIO using SAS® software Version 9.3 which meets the requirement as stated in the protocol.

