6. DEFINITIONS

6.1 Progression-Free Survival (PFS)

The duration of PFS, defined as the number of months from randomization to the earlier of progressive disease or death due to any cause. One month is considered 30.4375 days.

PFS (months) = (Date of Progression or Censoring – Date of Randomization + 1) ÷ 30.4375

Patients who meet one or more of the following conditions at the time of primary analysis will be censored:

- No screening or post-screening disease assessments unless death occurred prior to the first planned assessment.
- Initiation of a new anticancer therapy in the absence of documented progression.
- Death or progressive disease after missing 2 or more consecutively scheduled disease assessment visits
- Last known to be alive and progression-free on or before the data cut-off date

**Statistical Analysis Plan
SNDX-275-0602 (TRIO025)
DM-025-037**

The following table, adopted from FDA guidance “*Guidance for Industry Clinical Trial Endpoints for the Approval of Cancer Drugs and Biologics*” (May 2007) illustrates how the cases will be handled for primary analysis. If a patient is censored satisfying more than one criteria, the situation with the earliest date will be considered.

Table 1 – Primary Rules for Determining Date of Progression or Censor for Primary Progression-Free Survival

	Situation	Date of Progression or Censoring	Outcome
1	Death before first PD assessment	Date of death	Progressed
2	Death or disease progression between planned disease assessments	Date of death or first disease assessment showing disease progression, whichever occurs first	Progressed
3	No baseline tumor assessments	Date of randomization	Censored
4	New anticancer treatment started (in absence of documented progression)	Date of last radiological assessment of measured lesions prior to the start of the new anticancer treatment	Censored
5	Death or progression after more than 2 or more consecutive visits	Date of last radiological assessment of measured lesions without documented disease progression that is before the first missed visit	Censored
6	Last known to be alive and progression-free on or before the data cut-off date	Date of last radiological assessment of measured lesions	Censored

The following sensitivity analyses will also be provided:

Table 2 – Progression-Free Survival Sensitivity Analysis

**Statistical Analysis Plan
SNDX-275-0602 (TRIO025)
DM-025-037**

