6.2 Objective Response Rate (ORR)

ORR is defined as the crude proportion of patients achieving a best overall response of CR or PR assessed using RECIST 1.1. The best overall response assessed using irRECIST will also be analyzed separately and the corresponding ORR will be calculated. The overall response will be determined locally by the investigator at each scheduled assessment.

Per protocol (Section 10.3.1.3), partial or complete response should be confirmed by a repeat tumor imaging assessment not less than 4 weeks from the date the response was first documented.

The following table will be followed to assign a best overall response based on the achievement and confirmation of two consecutive assessments according to RECIST 1.1:

Overall response First time point	Overall response Subsequent time point (at Least 4 Weeks Later)	Best Overall Response
CR	CR	CR

**Statistical Analysis Plan
SNDX-275-0602 (TRIO025)
DM-025-037**

Overall response First time point	Overall response Subsequent time point (at Least 4 Weeks Later)	Best Overall Response
CR	PR	PR
CR	SD	SD
CR	PD	PD
CR	NE	SD
PR	CR	PR
PR	PR	PR
PR	SD	SD
PR	PD	PD
PR	NE	SD

$$ORR_{RECIST1.1} = \frac{\# \text{ of patients with best overall response as CR or PR}}{\text{Total number of patients}}$$

Similarly, irCR or irPR based on irRECIST will also be confirmed.

The following table is therefore used for best overall response based on irRECIST:

Overall response First time point	Overall response Subsequent time point (at Least 4 Weeks Later)	Best Overall Response
irCR	irCR	irCR
irCR	irPR	irPR
irCR	irSD	irSD
irCR	irPD	irPD
irCR	irNE	irSD
irPR	irCR	irPR
irPR	irPR	irPR
irPR	irSD	irSD
irPR	irPD	irPD
irPR	irNE	irSD

And ORR based on irRECIST is calculated as follows:

$$ORR_{irRECIST} = \frac{\# \text{ of patients with best overall response as irCR or irPR}}{\text{Total number of patients}}$$

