10.8.3 CBR

The analysis of CBR will be based on the methods described above for ORR.

10.8.4 OS

The analysis of OS will be based on methods described above for PFS.

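### Protocol and SAP time stable disease for the clinical benefit rate from different starts to different ends, and with a scan due at week 24 the choice reclassifies about two to three patients per arm

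*SAP*

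**What the plan says.** Protocol 13.5.5 (Efficacy Analyses) defines the SD component of CBR this way: "Stable disease will be measured from the start date of study treatment until the criteria for progressive disease is first met". SAP 6.3 uses a duration "measured from the date of randomization to the last date where SD is reported". The 24-week threshold is the same in both, and SAP 6.3 carries its rule over to the irRECIST version.

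The Protocol synopsis schedules scans "then every 6 weeks (+/- 3 days) through week 36 (Weeks 6, 12, 18, 24, 30, 36"), and Protocol 6.1 has them "performed every 6 weeks (+/-3 days) (Week 6, Week 12, etc.) beginning at C1D1". Protocol 9.1 allows up to 3 business days between randomization and first dose.

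SAP 6.2 supplies a table that "will be followed to assign a best overall response based on the achievement and confirmation of two consecutive assessments". It gives a PR followed by a non-evaluable (NE) scan a best overall response of SD.

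CBR is a secondary endpoint compared between arms. SAP 10.8.3 states: "The analysis of CBR will be based on the methods described above for ORR". Protocol 13.5.5 tests endpoints other than PFS at one-sided 0.1.

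**The concern.** Both ends of the clock differ. The start differs by only a few days. The end differs by about one scan interval: the protocol clock runs on to the scan that shows progression, while the SAP clock stops at the last scan read as SD. With a 24-week threshold and a scan due at week 24, that interval decides whether a patient counts. The reported CBR therefore depends on which document the programmer follows, and two defensible definitions would be available once the data are unblinded.

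There is a secondary consequence. Read literally, the SAP end point passes over scans read as CR or PR. A patient whose response is not confirmed, and whose best response becomes SD under SAP 6.2, can then have her SD duration cut off before that response.

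**Working it through.** Neither document states a CBR rate or a CBR sample size, so there is no plan figure to reproduce. The check applies both clocks to scan sequences and then sizes the difference.

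**Inputs**
- Threshold: 24 weeks = 168 days (SAP 6.3).
- Scans at weeks 18, 24 and 30 = Days 126, 168 and 210 from C1D1; week-24 window Days 165–171 (Protocol synopsis and 6.1).
- Lag from randomization to first dose: 3 business days at most (Protocol 9.1), or 0 to about 5 calendar days if a weekend but no public holiday intervenes.
- Planning medians 4 and 7 months, 35 per arm (Protocol 13.1.2, SAP 5.2.2); one month = 30.4375 days (SAP 6.1).
- Assumed: exponential PFS; days counted as elapsed days; interval edges taken at nominal scan days; failures detected at the next scan. PFS failures include deaths (SAP 6.1: "defined as the number of months from randomization to the earlier of progressive disease or death due to any cause"), so deaths are counted here as progression. Confirmed responders, who have benefit under both rules, are not removed.

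**Sequences**

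| Scans | SAP duration (lag 0 / 5 days) | Protocol duration | Result |
|---|---|---|---|
| SD to week 18, PD at week 24 (Day 168) | 126 / 131 | 168 | SAP fails, protocol passes: group (a) |
| SD at Day 165, PD at week 30 | 165 / 170 | 210 | SAP fails with no lag, protocol passes: group (b) |
| SD at week 24 (Day 168), PD at week 30 | 168 / 173 | 210 | both pass |
| SD to week 18, PR at week 24, NE at week 30, no later SD | 126 / 131 | at least 168 | SAP fails, protocol passes |
| as above, then SD at week 36 | 252 / 257 | at least 252 | both pass |

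**Size of groups (a) and (b)**

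S(t) = exp(−ln 2 × t / median), with medians of 4 × 30.4375 = 121.75 days and 7 × 30.4375 = 213.06 days. Differences use unrounded values.

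| | Control | Experimental |
|---|---|---|
| S(126) | 0.4880 | 0.6637 |
| S(168) | 0.3843 | 0.5789 |
| S(210) | 0.3025 | 0.5050 |
| Failure, weeks 18–24 | 0.1038 | 0.0848 |
| × 35: group (a) if every week-24 scan is on or after Day 168 | 3.63 | 2.97 |
| Failure, weeks 24–30 | 0.0817 | 0.0739 |
| × 35: group (b) if every week-24 scan is on Days 165–167, no lag | 2.86 | 2.59 |

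These two maxima need opposite scan timing and cannot occur together. With scan days uniform over Days 165–171, 4/7 of scans fall on Days 168–171 and 3/7 on Days 165–167:
- Group (a): 3.63 × 4/7 = 2.08 control; 2.97 × 4/7 = 1.70 experimental.
- Group (b), no lag: 2.86 × 3/7 = 1.23; 2.59 × 3/7 = 1.11.
- Total: about 3.3 and 2.8 patients. Divided by 35, that is 9.4 and 8.0 points of CBR.
- Lag of 3 days or more: Day 165 + 3 = 168, so group (b) vanishes, leaving 2.1 and 1.7 patients (5.9 and 4.8 points).

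If deaths and confirmed responders were 20% of these failures (assumed), the no-lag totals fall to 3.3 × 0.8 = 2.6 and 2.8 × 0.8 = 2.2.

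**Late unconfirmed response**

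PR at week 24 then NE has best response SD in the SAP 6.2 table, so she can enter CBR only through the 24-week SD rule. Her last scan read as SD is Day 126 and she fails. A patient with plain SD at Day 168 and PD afterwards passes. The documents give no frequency for this pattern. About 35 × 0.3843 = 13.4 control and 35 × 0.5789 = 20.3 experimental patients are progression-free at week 24, so each 1% of them with the pattern is 0.13 and 0.20 patients.

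**The case against.** The SAP rule can be defended. Ending SD at the last SD scan is conservative and computable, and one sentence acknowledging the departure from Protocol 13.5.5 would remove the contradiction. That stands, and the fix allows for it. The SAP was also written "according to SNDX-275-0602 (TRIO025) protocol version 1.0", so the mismatch may be version drift. That could explain the difference but does not reconcile the texts.

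The counts are approximate. They include deaths, which the protocol's SD clock does not mention, and confirmed responders, who do not switch. They also depend on scan timing and start lag, which the documents bound but do not fix.

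The PR-then-NE case needs a narrow sequence and a literal reading. A programmer could date the SD assigned by the SAP 6.2 table to the week-24 scan itself. SAP 6.3 does not settle this, so the case is secondary and probably rare.

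A reader might go further in two ways. One is to infer bias between the arms or damage to the primary result. The documents do not support that: the phase is double-blind, one rule would apply to both arms, and PFS has its own definition. The other is to add PR at week 24 followed by PD as a further failure of the SD clock. Any failure there comes from the best-response table, which assigns PD to that pair, and is a separate question.

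**Conclusion.** The contradiction is certain on the text: start and end of the SD duration both differ, and nothing reconciles them. The end date does most of the work. The start date matters only for patients within a few days of the threshold.

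The size is a model estimate, and it is not zero at either extreme of scan timing. If all week-24 scans fall on or after Day 168, up to about 3.6 control and 3.0 experimental patients switch. If all fall on Days 165–167 with no lag, up to about 2.9 and 2.6 do. In a comparison of 35 per arm that is visible. The point should be settled, but it concerns one secondary endpoint and does not touch the design.

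**What to change.** Before unblinding, put one rule in Protocol 13.5.5 and SAP 6.3, or have the SAP state explicitly that it departs from 13.5.5:

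- SD duration for CBR runs from randomization, as for PFS, to the last assessment without progression, whether read as CR, PR or SD. An unconfirmed CR or PR whose best response becomes SD is then judged on that duration.
- A week-24 scan within its ±3-day window satisfies the 24-week threshold. This belongs in the main rule, because without it group (b) still depends on a few days of scan timing and start lag.
- The same wording applies to the irRECIST version.

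The cost is wording and minor programming; no new data are needed. CBR will be lower than under the protocol rule for patients with progression first seen at week 24. It will be slightly higher than under the current SAP rule for early in-window scans and late unconfirmed responders.
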